1.5.2 Anticipated Risks

ONT sequencing will be utilized alongside current SCs. We will use SC to ensure that the care patients receive will be no worse than current practice. In other words, culture will ensure that ONT only improves patient care and outcome. In the event that ONT results and culture assessment contradict, the care plan will prioritize the results of standard culture in the event of treatment failure (Table 3). The risks associated with participation in this study are no greater than for those patients not on the study also undergoing identical operations. The only therapeutic interventions this trial includes is alteration or cessation of postoperative antimicrobial therapy based on either ONT or SCs. In order to minimize any theoretical risks in the ONT arm, such as missed microbial species and/or antibiotic resistance phenotype or ineffective antibiotic regimen, SC data will be utilized in both arms and antibiotic therapy will be adjusted if SCs suggest broader coverage (Table 3). There will be no alteration in the standard clinical postoperative care of patients in this study.

Table 3: Incorporation of ONT results in clinical management decisions

ONT Result	Clinical management decision
A negative ONT result	Discontinue antibiotics after 24 hours of peri-operative coverage
A positive ONT result for a single pathogen typical of biliary or gastrointestinal flora	Adjust and/or narrow antibiotic therapy to cover single pathogen. If single pathogen deemed clinically insignificant (ie. lactobacillus), discontinue antibiotics after 24 hours of peri-operative coverage.
A positive ONT result for multiple pathogens	Adjust and/or narrow antibiotic therapy to cover all pathogens, excluding those deemed clinically insignificant. If all pathogens are considered clinically insignificant, discontinue antibiotics after 24 hours of peri-operative coverage.
A positive ONT result positive for rare or unexpected flora	Adjust and/or narrow antibiotic therapy to cover rare or unexpected flora, excluding those deemed clinically insignificant.
ONT results different from SC	Adjust and/or narrow antibiotic therapy to cover pathogens found in ONT results, excluding those deemed clinically insignificant. SC results to only be considered in the event of treatment failure with antibiotic therapy targeted towards ONT results.

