2.1 General Design

This will be a prospective 1:1 randomized controlled trial with the following study arms:

Arm 1: Patient Group 1

Standard Care Only. Patients will undergo intra-operative bile aspiration (as is routinely performed) with SC of the aspirate. All patients will receive standard prophylactic antibiotics according to practice standards and will be continued for up to 5 days as is routine. If bile cultures are positive, antimicrobials will be continued for a complete 10-day course of antibiotics (Figure 2).

Arm 2: Patient Group 2

Standard Care + ONT. Patients will undergo intra-operative bile aspiration (as is routinely performed) with standard cultures AND ONT sequencing of the aspirate. All patients will receive standard prophylactic antibiotics according to practice standards. ONT sequencing results will be made available to providers through electronic medical record (EMR) and team electronic notifications. Patients with negative ONT results will be taken off the standard prophylactic antibiotics and patients with positive ONT results will have antimicrobial therapy adjusted according to ONT sequencing results. However, if SCs are positive or suggest alternative/broader coverage then these results

will guide therapy and not ONT results. If bile cultures are positive, antimicrobials will be continued for a complete 10-day course of antibiotics (Figure 2).

[figure not shown]

Figure 2: A schematic diagram of our proposed study to investigate the use of Oxford nanopore sequencing to detect and characterize biliary microbial contamination

The study will include patients undergoing elective pancreaticoduodenectomy or total pancreatectomy for any clinical indication. Patients will be excluded from the study if they are < 18 years of age, enrolled in any similar clinical trials involving use of peri-operative antibiotics, are undergoing distal pancreatectomy, or undergoing emergency total pancreatectomy or emergency pancreaticoduodenectomy (Table 4). Following recruitment to the study, patients will be randomly assigned intraoperatively/post-operative to either the control group (Arm 1) or the interventional group (Arm 2). We will use stratified randomization with age (below 65 years vs 65 years and above), sex, operation type (pancreaticoduodenectomy vs total pancreatectomy), biliary stenting (yes vs no), and patient ASA score as stratification factors.

Table 4: Patient inclusion and exclusion criteria for the clinical trial

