After sequencing data is gathered, samples will be destroyed. The data results from the ONT sequencing testing will be entered into EMR as a research clinic note for documentation and results will additionally be emailed to the medical providers on the care team. Decisions on antibiotic regimen will be made with the assistance of Surgical Clinical Pharmacy with changes in regimens as deemed appropriate based on standard cultures and ONT results, as described in Table 5. A negative ONT result will result in discontinuation of perioperative antibiotics after 24 hours while a positive ONT result will be used to guide early targeted antibiotic therapy (Table 5). With regards to early discontinuation of antibiotics, we are confident that this will not adversely impact patient care as our preliminary data demonstrated that ONT resulted in no false negative calls. However, as this is a new technology, SC will be performed alongside ONT, and if microbial growth is detected in the cultures, the clinician will have the option of reverting patient care to current standard of practice. This option will also be available in the event of treatment failure in patients with positive ONT results (Table 5).

Given that currently clinically available tests will be available to the care team with the additional ONT sequencing as supplemental data there will be minimal risk to subjects participating in this study.

Table 5 Incorporation of ONT results in clinical management decisions

ONT Result	Clinical management decision
A negative ONT result	Discontinue antibiotics after 24 hours of peri-operative coverage

A positive ONT result for a single pathogen typical of biliary or gastrointestinal flora	Adjust and/or narrow antibiotic therapy to cover single pathogen. If single pathogen deemed clinically insignificant (ie. lactobacillus), discontinue antibiotics after 24 hours of peri-operative coverage.
A positive ONT result for multiple pathogens	Adjust and/or narrow antibiotic therapy to cover all pathogens, excluding those deemed clinically insignificant. If all pathogens are considered clinically insignificant, discontinue antibiotics after 24 hours of peri-operative coverage.
A positive ONT result positive for rare or unexpected flora	Adjust and/or narrow antibiotic therapy to cover rare or unexpected flora, excluding those deemed clinically insignificant.

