ONT results different from SC	Adjust and/or narrow antibiotic therapy to cover pathogens found in ONT results, excluding those deemed clinically insignificant. SC results to only be considered in the event of treatment failure with antibiotic therapy targeted towards ONT results.

Databases Used

For the analysis of our endpoints, we are relying on sequence homology for two main tasks, mainly, (1) the identification of species and (2) identification of AMR phenotypes. For species identification, we use the refseq genome database (downloaded on 12/18/2020) with all data from the following higher order taxa groups included: human, protozoa, viral, bacterial, and fungal. For the identification of AMR phenotypes, we use the ResFinder database (downloaded on 06/04/2021, version 4.1) which contains the acquired chromosomal resistance genes, ensuring we know which species is carrying a given resistance gene. For plasmid AMR gene identification, we will use the PlasmidFinder-specific database (downloaded on 7.14.2021/version 2.0.1) and the CARD data (downloaded on 07/07/21, version CARD 2020). These databases undergo regular updates since they were first developed. To ensure the analysis remains consistent throughout the study, databases will not be updated for the duration of the study. In the unlikely event that we require a software/ database update in order to run these tools (compatibility issues with future institutionally required OS update, inability to restore databases from archives after computational disaster), we will validate any newer versions of the database and/or algorithms using the data and culture gold standards from our published study and recently collected data and will only proceed if we have comparable performance in accuracy for species and AMR identification.

Patient Follow-up and Safety Monitoring

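### Arm 2 has two incompatible instructions for ONT-positive patients whose culture differs: follow culture at once, or wait for treatment failure

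*Combined protocol and SAP*

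**What the plan says.** **Section 2.1 General Design, Arm 2.** ONT-positive patients have therapy set by the ONT result, but "if SCs are positive or suggest alternative/broader coverage then these results" are to direct treatment instead of ONT. No treatment failure is required. A positive culture means a full 10-day course.

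**Table 3 (section 1.5.2) and Table 5 (section 2.1), last row.** The wording is the same in both. When ONT and culture differ, the pathogens found by ONT are treated, with "SC results to only be considered in the event of treatment failure with antibiotic therapy targeted towards ONT results".

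**Section 1.5.2 text.** It holds both rules and cites Table 3 for each. When the two tests contradict, "the care plan will prioritize the results of standard culture in the event of treatment failure (Table 3". Two sentences later it says that "SC data will be utilized in both arms and antibiotic therapy will be adjusted if SCs suggest broader coverage (Table 3". Table 3 supports only the first. The same section gives the assurance "We will use SC to ensure that the care patients receive will be no worse than current practice".

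**Section 2.1, text before Table 5.** Regimens are changed with pharmacy help, "as deemed appropriate based on standard cultures and ONT results, as described in Table 5". If cultures grow, "the clinician will have the option of reverting patient care to current standard of practice". It adds: "This option will also be available in the event of treatment failure in patients with positive ONT results".

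**The concern.** A clinician with an ONT-positive patient and a differing culture has two written instructions that cannot both be followed. Under the tables, action on a cultured organism or a resistance that ONT missed waits until the patient fails treatment. Current practice (section 1.1) tailors therapy to a positive culture, and section 1.5.2 offers culture as the protection against missed organisms and resistance. Following the tables exactly removes that protection in the patients who need it.

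The Arm 2 rule has a risk of its own. It puts culture in place of ONT, so, read literally, a positive culture would end cover for organisms that only ONT found. These may include Candida, whose late detection is one of the plan's own reasons for the trial.

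A lesser point is interpretation. Antibiotic duration, number and spectrum are the primary outcomes (section 5.3), and this rule helps to set them in Arm 2. The strategy under test is therefore not uniquely defined.

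**Working it through.** **Step 1. The rules side by side**

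| Arm 2 patient | Arm 2 text, section 2.1 | Tables 3 and 5, and text before Table 5 | Result |
|---|---|---|---|
| (a) ONT positive; culture shows an organism or resistance that ONT-directed therapy does not cover | Change to culture-guided therapy now | Stay on ONT-directed therapy until it fails | Direct conflict |
| (b) ONT and culture positive; ONT found further organisms | Culture directs therapy, ONT does not | Cover the ONT organisms | Direct conflict |
| (c) ONT negative; culture grows | Culture directs therapy | Clinician may revert; no failure needed | Mandatory versus optional only |
| (d) ONT positive; culture negative | Treat to ONT | Treat to ONT | None |

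In (c), the last table row cannot operate as a delay, because there is no ONT-targeted therapy to fail.

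**Step 2. How often (a) can arise**

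Inputs from section 1.4 and Table 2: 42 pilot patients, 23 culture-positive; Enterococcus cultured in 17 and found by both methods in 13.

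- The plan's own figure: 13/17 = 76.5%, as section 1.4 states for Enterococcus.
- Missed by ONT: 17 − 13 = 4 patients; 4/42 = 9.5%.
- Exact (Clopper-Pearson) 95% limits: lower = Beta quantile (0.025; x, n − x + 1), upper = Beta quantile (0.975; x + 1, n − x). With x = 4 and n = 42 these are 2.7% and 22.6%.
- At that rate in 70 Arm 2 patients: 70 × 4/42 = 6.7, about 7.

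Other misses in Table 2 are Serratia 3 − 1 = 2, and one each of Enterobacter, Streptococcus, Citrobacter freundii, Pseudomonas and S. aureus. With Enterococcus that makes 11. If all 11 were in different patients, which is an assumption, the share would be 11/42 = 26%. Overlap is possible, so only the 4 are firm.

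Section 1.4 says that ONT identified every contamination case. If that means all 23 culture-positive patients, the 4 were ONT-positive and belong to (a): 4/23 = 17.4% (exact 95% CI 5.0% to 38.8%). On the same reading (c) did not occur: 0/23, upper limit 1 − 0.025^(1/23) = 14.8%.

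For resistance, ONT predicted 81% of the phenotypes seen by culture, so 19% were not predicted.

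**Step 3. How often (b) can arise**

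ONT-only detections in Table 2 (ONT positive minus positive by both): Streptococcus 19 − 15 = 4, Klebsiella 14 − 11 = 3, Candida 7 − 5 = 2. Counts are used because the printed ONT percentages for the first two do not match them.

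Whether these patients were culture-positive is not stated. Section 1.1 says that ONT agreed perfectly when cultures were negative. On that reading they were all culture-positive, and Streptococcus alone gives 4/42 = 9.5%. Section 6.1 instead assumes 77% ONT positivity against 54% for culture. At 77%, 0.77 × 42 = 32 patients would be ONT-positive, leaving 32 − 23 = 9 culture-negative patients who could hold the ONT-only detections. The pilot frequency of (b) from Streptococcus therefore lies between 0 and 9.5%, depending on which statement applies.

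**Step 4. A related clash**

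The single-pathogen and multiple-pathogen rows of Tables 3 and 5 stop antibiotics at 24 hours when organisms are judged insignificant. The Arm 2 text requires 10 days for any positive culture, without that exception.

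**The case against.** The strongest case for leaving the text alone is practical. Culture results appear in the medical record for both arms (section 2.1), care is open-label, pharmacy helps to choose regimens, and inpatients are watched around the clock (section 7.2, Medical Monitoring). A sensible team would probably act on a worrying culture. A missed species may also be covered already by the drug chosen. Figure 2 and the trial schematic numbered Figure 3 are not available to this review and may show an intended order.

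These points lower the risk but do not settle the rule. Seeing the culture does not say which instruction governs. The sentence that allows judgement refers to Table 5, which contains the conflicting row. A figure could show intent, but the contrary text in sections 1.5.2 and 2.1 would remain. What stands is that the number of patients whose treatment would change cannot be derived from the documents.

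A reader might go further and infer that every discordant Arm 2 patient, including one with a negative ONT result, must wait for treatment failure. The documents do not say so: for ONT-negative patients the text before Table 5 allows reversion once culture grows.

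**Conclusion.** The plan is wrong as written and needs correcting. In groups (a) and (b) the Arm 2 text and the tables give opposite instructions, section 1.5.2 repeats the conflict, and no visible text sets precedence. For ONT-negative patients with culture growth the gap is only mandatory versus optional reversion. ONT-positive, culture-negative patients are not affected.

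The firm size is 4/42 (9.5%, 2.7% to 22.6%) with a cultured Enterococcus that ONT missed. Placing those patients in group (a) assumes that the 100% detection claim covers all culture-positive patients. The figure is one of discordance in a small pilot.

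Two stronger conclusions are tempting. One is that about a tenth of Arm 2 would be under-treated, or that antibiotic duration would shift by a known amount. Table 2 does not show which drugs would have covered the missed organisms, and no course length is given for ONT-directed therapy, so neither follows. The other is that the randomised comparison is invalid. It is not: outcomes are defined and allocation is unaffected. What is unclear is which Arm 2 strategy the result would describe.

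**What to change.** Use one additive rule in section 1.5.2, the Arm 2 text, the text before Table 5, and Tables 3 and 5:

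> ONT guides therapy until culture results return. If culture grows a clinically significant organism, or shows a resistance, that current therapy does not cover, broaden or restart antibiotics at once without waiting for treatment failure, and keep cover for clinically significant organisms found by ONT. A positive culture with a clinically significant organism is treated to a complete 10-day course. A negative culture does not by itself override a positive ONT result.

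Specific edits:

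- **Section 1.5.2:** replace the whole sentence on contradictory results. Deleting only its treatment-failure condition would give a negative culture priority over a positive ONT result. On the section 6.1 rates that group could be 0.77 − 0.54 = 23 points, or 0.23 × 70 = about 16 Arm 2 patients.
- **Section 2.1, Arm 2:** replace the words that set ONT aside, and limit the 10-day rule to clinically significant organisms.
- **Section 2.1, before Table 5:** replace the sentence giving the option to revert and the treatment-failure sentence after it.
- **Tables 3 and 5:** replace the last row, and make the 24-hour stop rows subject to the same rule.

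The cost is a wording amendment, but one that changes a treatment rule, so the IRB and FDA notification described under deviations from the investigational plan (section 7.1.3) applies. Sample size, endpoints and data collection do not change.

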Inclusion Criteria	
 • > 18 years of age • Scheduled for elective total pancreatectomy or pancreaticoduodenectomy
Exclusion Criteria	
 • < 18 years of age

	
• Emergency total pancreatectomy or pancreaticoduodenectomy• Patients scheduled for distal pancreatectomy• Women who are pregnant• Patients without the cognitive capacity to consent• Patients enrolled in similar clinical trials involving use of perioperative antibiotics
--	--

Bile will be collected via bile duct aspiration. Bile aspiration will be performed with a 16-gauge needle and 3 cc syringe prior to bile duct division (Figure 3), and aspirated material will be aseptically transferred into sterile aerobic and anaerobic transport vials. Samples will be concurrently transported to the Pathology lab and the microbiome lab to undergo SC techniques and ONT sequencing, respectively. Standardization of bile collection and surgical procedure will be assured as all surgeries will be performed by the same lead surgeon, [name]. Surgical variables that have been associated with increased SSI risk will be recorded. This will include patient sex, age, BMI, ASA score, the volume of blood loss, whether the patient had a biliary stent inserted prior to surgery, closure technique, and whether vascular reconstruction was performed during surgery.

[figure not shown]

Figure 3: Collection of intraoperative bile aspirate during pancreatic head resection (total pancreatectomy, pancreaticoduodenectomy)

SCs obtained from intraoperative bile aspiration for both study arms will be performed in compliance with clinical standards. This is routinely performed by the Pathology lab and no changes to these protocols are necessary (see Supplementary Materials S1 – S6) for culture methods and AST protocols). Results will be reported in the EMR which will be accessible by the clinical team, as is the current clinical practice. ONT sequencing for those assigned to Study Arm 2 will be performed on a 1cc liquid bile sample collected fresh from the operating room after specimen release from the Pathology lab. Approval from our institutional TRAG

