4.3 Masking/Blinding of Study

This is an open, randomized trial. Subjects and study team members will not be blinded.

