5.2 Sample Collection Visit

Following enrollment procedures, 2 cc of residual bile collected during surgery will be aliquoted into cryovial and placed on ice (not frozen). It will be picked up by the study team at the time of collection for ONT sequencing. Tissue Request Acquisition Group (TRAG) approval will be requested for managing of samples. The sample will be aliquoted from the clinical collection and so collection will not add additional time to the surgery procedure. Participants will be randomized in Medidata Rave to a study arm based on operation type and pre-operative biliary stenting using a dynamic stratification. Participants will be randomized in a 1:1 ratio.

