6.2 Statistical Methods

Descriptive Statistics

The primary analysis of this study will be a modified intention to treat analysis (ITT), performed to determine how use of ONT changed patient treatment, i.e. did use of ONT improve antibiotic stewardship. Proportions of patients with detection of microbes of interest will be estimated along with exact 95% binomial confidence intervals. Comparisons of the proportions between the two study arms will be compared using Fisher's exact test or Chi-square test as appropriate. We will calculate the time from randomization to first microbial detection within a patient. We will report the mean difference in time to first microbial detection within 96 hours post randomization in both treatment arms, together with a 95% confidence interval. Comparison of time to first microbial detection within 96 hours post randomization, will be performed using Wilcoxon rank sum test or two sample t-test as appropriate. If there are any baseline imbalances in demographic or clinical variables between the two groups, we will perform the analysis using univariable and multivariable linear regression adjusting for these variables with imbalances as possible confounders. Duration of antibiotics, total number of different antibiotics, and broad-spectrum antibiotics vs narrow-spectrum antibiotics administered in the two arms will be compared to determine if use of ONT improved antibiotic stewardship by significantly reducing the duration of perioperative antibiotics and use of broad-spectrum antibiotics

Secondary analysis will evaluate SSI's will be evaluated and classified using ACS NSQIP definitions and data collected will include mortality rate, SSI incidence rate, ICU length of stay, total length of hospital stay, need for interventional procedures, and hospital readmission. Statistical analysis will be performed by the study team to determine if use of ONT significantly improved patient outcome compared to patients who received standard of care

only. The secondary endpoint of the study is a binary endpoint i.e. whether patients develop SSI (yes, no). Association between the secondary outcome and predictor variables will be assessed using univariable and multivariable logistic regression.

In both primary and secondary analysis, the following variables will be assessed for inclusion in the regression models

- Age at time of surgery DOB
- BMI at time of surgery RAVE calculate
- Sex

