- Diabetes mellitus co-morbidity at time of surgery (clarifications needed for data collection)
- Cancer diagnosis
- ASA score at time of surgery
- Administration of chemotherapy prior to surgery (from what timepoint or date of last chemo?)
- Presence of biliary stent at time of surgery
- Blood loss during surgery
- Length of surgery (skin to skin, open to close?)
- Vascular reconstruction (arterial, venous) during surgery
- Closure technique
- Pancreatic leak risk score (when done? In record?)
- Surgical drains (what is needed)
- Post-op TPN

Variables with p-values less than 0.15 will be considered as potential candidates for a multivariable model. We will report odds ratios and 95% confidence interval. The area under the receiver operating characteristic (ROC) curve will be estimated as a measure of the ability of the model to discriminate between patients who had SSI within 90 days versus those who did not. An area under the ROC estimate of 0.7–0.8 will be regarded as acceptable, 0.8–0.9 will be regarded as excellent, and more than 0.9 will be regarded as outstanding.

We will also assess cost effectiveness of using ONT compared to SC. To achieve this, we will compare the cost to perform SC testing and ONT testing against costs associated with post-operative patient care. This will include the total cost to administer perioperative antibiotics, costs associated with length of hospital stay, and the costs associated with the need of additional procedures and tests associated with SSI (i.e. post-operative SC and antibiotic susceptibility testing, additional antibiotics, wound debridement, abdominal abscess drainage, CT scan, US scan).

For continuous variables, t-test will be performed and for binary variables chi-square or fisher's exact testing will be performed as appropriate. Additional analysis will be performed as necessary to determine differences in study arms. Should additional analysis beyond the scope of our abilities is necessary then a statistician will be employed.

Inpatient related costs associated with each intervention arm will be analyzed and compared with the assistance of the Robert D. and Patricia E. Kern Center for Science of Health Care in order to understand the economic impact of each intervention arm.

Handling of Missing Data

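### Section 6.2 lets post-operative TPN, and operative variables that may be settled after allocation, enter the regression models that compare the arms

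*Combined protocol and SAP*

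**What the plan says.** **When the arm is assigned.** Section 2.1 (General Design) says "patients will be randomly assigned intraoperatively/post-operative to either the control group (Arm 1) or the interventional group (Arm 2". Section 5.2 places the step at the sample collection visit: "Participants will be randomized in Medidata Rave to a study arm based on operation type and pre-operative biliary stenting using a dynamic stratification". Neither section fixes a single moment. Section 2.1 also puts bile collection early in the operation: "Bile aspiration will be performed with a 16-gauge needle and 3 cc syringe prior to bile duct division".

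**Who knows it.** Section 4.3 describes an open trial: "Subjects and study team members will not be blinded". No text withholds the arm from the operating team until closure. All operations have the same lead surgeon (Section 2.1).

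**What may be adjusted for.** Section 6.2 states: "In both primary and secondary analysis, the following variables will be assessed for inclusion in the regression models". The list mixes patient characteristics (age, sex, BMI, ASA score, stent) with blood loss, length of surgery, vascular reconstruction, "Closure technique", "Surgical drains (what is needed" and post-op TPN. Variables with p below 0.15 become candidates for the multivariable model. No rule excludes variables that arise after allocation.

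**What rests on it.** The success criteria under the primary and secondary objectives (Section 2.2) are both stated for results corrected for key covariates.

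**The concern.** Adjustment in a randomised comparison is safe for variables that the assignment cannot have influenced. Post-op TPN does not clearly meet that test. It is post-operative care and may be started because of complications. Those complications are part of what earlier tailored antibiotics are meant to prevent. Conditioning on TPN can then do two things:

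- block part of a real effect on SSI, because some of the effect runs through complications that TPN marks;
- create an apparent arm effect where none exists, if an unmeasured severity factor drives both TPN and the outcome.

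A screen on p-values makes entry more likely the more closely TPN tracks the outcome.

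The operative variables are a conditional case. For a patient allocated after surgery they precede allocation. For a patient allocated around bile collection, drains and closure are still to come, and blood loss and length of surgery are incomplete. The same covariate could therefore be pre-allocation for some patients and post-allocation for others. Section 2.1 itself treats closure technique, blood loss and vascular reconstruction as SSI risk variables: "Surgical variables that have been associated with increased SSI risk will be recorded".

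**Working it through.** **Step 1: order of events, from the text.**

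| Candidate in 6.2 | If allocated during surgery | If allocated after surgery |
|---|---|---|
| Age, sex, BMI, ASA score, stent | before allocation | before allocation |
| Blood loss, length of surgery | not complete at allocation | before allocation |
| Vascular reconstruction | may be before or after | before allocation |
| Drains, closure technique | after allocation | before allocation |
| Post-op TPN | after allocation | after allocation on the natural reading |

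The last cell follows because Section 5.2 ties randomisation to sample collection and Section 2.1 requires fresh bile. It is not certain, since no latest time for a post-operative allocation is set. The share of patients allocated before closure cannot be derived and could be anything from 0 to 100%.

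**Step 2: the plan's own figure.** Section 6.1 gives 66 per group for 54% against 77%, alpha 0.05 and power 80%. The two-sided pooled-variance formula without continuity correction gives 66, so the figure reproduces. It does not bear on this point and the fix leaves it unchanged.

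**Step 3: illustration for SSI (all inputs assumed).** Let a complication occur in 35% of controls and 20% of the sequencing arm. Let SSI be 50% with it and 12% without, and TPN 50% with it and 8% without. SSI and TPN are independent given the complication.

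- SSI, control: 0.35×0.50 + 0.65×0.12 = 0.253
- SSI, sequencing: 0.20×0.50 + 0.80×0.12 = 0.196
- Unadjusted odds ratio: (0.196/0.804) / (0.253/0.747) = 0.72

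Within TPN strata:

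- TPN yes: P(complication | TPN) is 0.175/0.227 = 0.771 in control and 0.100/0.164 = 0.610 in sequencing. SSI = 0.12 + 0.38×that probability, giving 0.413 and 0.352. Odds ratio 0.77.
- TPN no: 0.175/0.773 = 0.226 and 0.100/0.836 = 0.120, so SSI is 0.206 and 0.165. Odds ratio 0.76.
- Logistic model with arm and TPN, fitted to the exact cell probabilities: odds ratio 0.766, which rounds to 0.77.

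Shift on the log-odds scale: ln(0.766/0.720) = 0.062. Standard error of the unadjusted log odds ratio at 70 per arm: √[1/(70×0.253) + 1/(70×0.747) + 1/(70×0.196) + 1/(70×0.804)] = 0.41. The shift is about 0.15 standard errors.

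Sensitivity to how closely TPN tracks the complication:

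| TPN with / without complication | Adjusted odds ratio | Shift in standard errors |
|---|---|---|
| 50% / 8% | 0.77 | 0.15 |
| 70% / 5% | 0.83 | 0.34 |
| 90% / 2% | 0.92 | 0.61 |

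If the complication rate is the same in both arms, the adjusted and unadjusted odds ratios are both 1 and there is no bias.

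**Step 4: illustration for antibiotic duration (all inputs assumed).** Simulated trials of 140 patients, 2,000 per setting, with no true arm effect on days. Control TPN is roughly a quarter. An unmeasured severity factor adds 1 to the log-odds of TPN and 2 days of antibiotics per SD. The residual SD is 2 days.

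| Arm effect on TPN (log-odds) | Spurious arm effect after TPN adjustment (days) | Type I error at nominal 5% |
|---|---|---|
| 0 | about 0 | 4.9% |
| -0.5 | +0.14 | 6.4% |
| -1.0 | +0.23 | 7.6% |
| -1.5 | +0.30 | 8.9% |

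The unadjusted analysis stayed at about 5% throughout. TPN passed the p<0.15 screen in 88 to 95% of runs.

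**The case against.** The strongest reply is that Section 6.2 does not commit to adjusting for TPN. The variables are only to be assessed, and p<0.15 makes them only potential candidates. For the arm comparison, the text triggers regression on baseline imbalance, which TPN cannot be. The list follows a sentence on predictors of SSI and leads to an ROC curve, so much of it reads as a prediction model, where post-operative predictors matter less. Several entries still carry drafting queries, so the list is visibly unfinished.

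Much of that is fair. It limits the point without removing it. The list is expressly extended to the primary analysis, success is defined on corrected results, and nothing separates the prediction use from the treatment comparison. An analyst who follows the text could adjust the arm effect for TPN and be within the plan.

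On the operative variables the reply is stronger. A reader might infer that the surgeon knows the arm before closing and operates differently. The documents do not show this. Section 2.1 equally allows post-operative allocation, and nothing says that the arm is announced in theatre. Being open does not establish when the surgeon is told. The sequencing result takes a median of 14 hours (Section 1.1) and acts on post-operative antibiotics, so there is no obvious reason for closure or drains to change. Section 2.1 also describes collection and surgery as standardised under one lead surgeon. Unequal handling remains a possibility because no text rules it out.

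**Conclusion.** The point holds for post-op TPN: the plan as written permits the arm comparison to be adjusted for a variable that assignment may affect. For closure technique, drains, blood loss, length of surgery and vascular reconstruction it holds only for patients allocated during surgery, whose number is unknown.

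Two stronger readings are not supported. One is that surgical handling differs between arms. The other is that TPN follows allocation in every patient without exception, since no latest allocation time is set.

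The size is not known. Under the main assumed inputs the SSI odds ratio moves from 0.72 to 0.77, which would not be noticeable with 70 per arm. It grows if TPN tracks complications closely (0.92 at the extreme shown). For duration, type I error rose to at most 8.9% in the settings tried. Every one of these figures rests on assumptions, and the bias is nil if the arm does not affect TPN or its causes. The reason to act is that the remedy is nearly free and the corrected results decide success.

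**What to change.** 1. **Section 6.2.** Remove post-op TPN from the models that estimate the treatment effect. Limit adjustment there to variables fixed before the allocation is disclosed to the operating team. Report TPN by arm descriptively. It may stay in an SSI prediction model if that model is labelled exploratory and kept apart from the arm comparison.
2. **Sections 2.1 and 5.2.** State one disclosure point: the allocation is withheld from the operating team until skin closure. The sequencing laboratory may receive it at bile collection, so that sequencing is not delayed. The operative variables are then fixed before that team knows the arm, and become eligible for adjustment under item 1.

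Cost: one deletion, one sentence of restriction and a rule on who is notified when. The clinical team learns the arm somewhat later than it otherwise might, which matters little against a median of 14 hours to the sequencing result. Sample size and treatment are unchanged.
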